6.3 Measures to Minimize Bias: Randomization and Blinding

Randomization

The enrolled participants will be randomly separated into four groups (i.e., the co-administration group 1, co-administration group 2, staggered administration group 1 and staggered administration group 2) at a 1:1:1:1 ratio. Stratified Blocked Randomization will be carried out, taking the study site as a stratification factor. The independent randomization statistician will use SAS 9.4 software or later versions to generate a randomization code list. In order to minimize the probability of relevant persons being informed of the group, the paper randomization card with numbers will be used. For each eligible participant, after enrollment, the grouping information will be revealed, including the name of the vaccine and the site of vaccination.

Blinding

This study adopted an open-labelled design, it would not be possible to blind the participant group. However, during blood collection, it should be guaranteed the Phlebotomist/Study Nurse/Medical Technologist are not aware of the participant group to reduce bias. In addition, lab personnel will be completely blind during the laboratory assessment as each sample will be labelled with unique ID code without grouping information.

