9.3.4 Immunogenicity Analysis

Analysis for immunogenicity against Polio

Seroconversion rate and sero-protection rate on day 28 after the last vaccination of sIPV will be estimated, and the corresponding 95% CIs will be derived from Clopper Pearson method.

The difference of seroconversion rates between co-administration group and staggered administration group will be compared using Cochran-Mantel-Haenszel- χ^2 (CMH- χ^2) test stratified by study site. The CMH- χ^2 method will be used to calculate the rate difference between (group C1 and group S1) and 95% CIs. Non-inferiority will be concluded if the lower limit of the 95% CI of rate difference (co-administration group-staggered administration group) $>-10\%$.

The descriptive statistics, including GMT and GMFR and corresponding 95% CIs are employed to summarize the immunogenicity data. The t-tests after log transformation will be used to compare two groups. The GMT ratio between two groups and the corresponding 95% CIs will be estimated as well.

Analysis for immunogenicity against Diphtheria, Tetanus, Pertussis

Seropositivity/sero-protection rate against Diphtheria, Tetanus and Pertussis on day 28 after the last vaccination of DTP-HepB-Hib vaccine will be estimated and the corresponding 95% CIs will be derived from Clopper Pearson method. The difference of seropositivity/sero-protection rate between co-administration group and staggered administration group will be Cochran-Mantel-Haenszel- χ^2 (CMH- χ^2) test stratified by study site. The CMH- χ^2 method will be used to calculate the rate difference between (group C2 and group S2) and 95% CIs. Non-inferiority will be concluded if the lower limit of the 95% CI of rate difference (co-administration group-staggered administration group) $>-10\%$.

The descriptive statistics, including GMC and GMFR and corresponding 95% CIs are employed to summarize the immunogenicity data. The t-tests after log transformation will be used to compare two groups. The GMC ratio of two groups and the corresponding 95% CIs will be estimated as well.

Analysis for immunogenicity against HepB, Hib, Pneumococcal

Sero-protection rates at day 28 after the last vaccination will be estimated and the corresponding 95% CIs will be derived from Clopper Pearson method. The Chi-square tests/Fisher Exact test will be used

to compare the sero-protection rates between two groups.

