4.1 Overall Study Design

4.1.1 Overview of the Study

This is a multi-country, multi-center, open-labelled, randomized, controlled, extended phase III clinical trial. Totally 1440 healthy infants of 6 weeks old (42-47 days) for Bangladesh and of 6-8 weeks old (42-56 days) for Pakistan (Bangladesh and Pakistan, each includes 720 participants) are planned to be enrolled, and then randomized in a 1:1:1:1 ratio into four groups, i.e., co-administration group 1 (group C1), co-administration group 2 (group C2), staggered administration group 1 (group S1) and staggered administration group 2 (group S2).

Participants in group C1 and C2 will receive sIPV at 6,10,14 weeks old (at 4-week intervals), administered concomitantly with routine infant vaccine (may include Adsorbed Diphtheria-Tetanus-whole cell Pertussis-Hepatitis B and Haemophilus influenza type b conjugate vaccine (DTP-HepB-Hib), PCV or rotavirus vaccine in accordance with the local routine vaccination schedule). Participants in group S1 will receive sIPV at 6,10,14 weeks old, and receive routine infant vaccines at 8,12,16 weeks old (at 4-week intervals, respectively). Participants in group S2 will receive routine infant vaccines at 6,10,14 weeks old, and receive sIPV at 8,12,16 weeks old (at 4-week intervals, respectively). The sample size allocations, vaccination schedules and blood collections for each group

in different countries are shown in the tables (table 1 to table 3) below.

Table 1 Study Design for Each Group

Group	Sample Code	Size	Vaccination Schedule						Blood Collection Time	Antibody Tests Testing Item
			6 weeks	8 weeks	10 weeks	12 weeks	14 weeks	16 weeks		
C1	360	sIPV+			sIPV+			sIPV+	Baseline 18 Weeks	Neutralizing antibody against polioviruses of type 1,2,3
		Routine vaccines			Routine vaccines			Routine vaccines		
C2	360	sIPV+			sIPV+			sIPV+	Baseline 18 Weeks	Antibodies against Diphtheria, Tetanus, Pertussis (FHA, Pertactin, Pertussis toxoid), Hepatitis B, Hib, Pneumococcal antibodies*
		Routine vaccines			Routine vaccines			Routine vaccines		
S1	360	sIPV	Routine vaccines	sIPV	Routine vaccines	sIPV	Routine vaccines	sIPV	Baseline 18 Weeks	Neutralizing antibody against polioviruses of type 1,2,3
S2	360	Routine vaccines	sIPV	Routine vaccines	sIPV	Routine vaccines	sIPV	sIPV	Baseline 18 Weeks	Antibodies against Diphtheria, Tetanus, Pertussis (FHA, Pertactin, Pertussis toxoid), Hepatitis B, Hib, Pneumococcal antibodies*
Total	1440									

*Only for serotype 1, 5, 6B, 14, 19F.

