4.2 Randomization

Stratified blocked randomization was carried out in this study, taking the study site as a stratification factor. The independent randomization statistician used SAS 9.4 to generate a randomization code list. In order to minimize the probability of relevant participants being informed of the group, the paper randomization card with numbers will be used. For each eligible participant, after enrollment, the grouping information will be revealed, including the name of the vaccine and the site of vaccination.

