7.7 Immunogenicity Evaluation

➤ **Immunogenicity evaluation for Nab against polioviruses**

The following analysis will be performed for Nab against polioviruses of serotype I, II, III between **group C1 and group S1 at 28 days after last vaccination of sIPV**, respectively:

The seroconversion (4-fold increase) rate in all participants, SCR in seronegative participants at pre-vaccination, 4-fold increase rate in seropositive participants at pre-vaccination and SPR in all participants will be estimated in each group. Clopper Pearson method will be used to calculate 95% CIs and Cochran-Mantel-Haenszel- χ^2 (CMH- χ^2) test stratified by study site (including Bangladesh 01, Pakistan 01 and Pakistan 02) will be used to test the differences between the two groups. The CMH method will be used to calculate the rate difference between (group C1 - group S1) and 95% CIs. Non-inferiority will be concluded if the lower limit of the 95% CI of SCR difference between group C1 and Group S1 >-10%.

Analysis of covariance model will be modeled to analyze Nab level against polioviruses at 28 days after last vaccination of sIPV. In this model, the log-transformed Nab data against polioviruses at 28 days after last vaccination of sIPV will be included as dependent variable, the log-transformed Nab data before vaccination as a covariate, and treatment group (including C1 and S1) and study site (including Bangladesh 01, Pakistan 01 and Pakistan 02) are the fixed effect. From the model, the LS-adjusted log-transformed Nab level against polioviruses at 28 days after last vaccination of sIPV in each group and the difference between (group C1 - group S1) will be calculated. The adjusted GMT at 28 days after last vaccination of sIPV in each group, GMT ratio between (group C1/group S1), and its 95% CIs will be obtained after inverse log-transformation.

Descriptive statistics, including geometric mean and 95% CIs, for GMT and GMFR in all participants, seronegative participants at pre-vaccination and seropositive participants at pre-vaccination will be presented by groups. The group t-test after log-transformation will be used to compare the differences between groups. The ratio of GMT between groups and their 95% CIs will be estimated as well.

The forest plot of the post-vaccination seroconversion (4-fold increase) rate for all participants in comparison (group C1 and group S1) will be plotted.

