The reverse cumulative distribution plot of antibody titers at pre- and post-vaccination time points will be plotted.

The above analysis will be based on the FAS and PPS.

➤ **Immunogenicity evaluation for IgG antibodies against pertussis**

The following analysis will be performed for IgG antibodies against PT, FHA and PRN of **group C2 and group S2 at 28 days after last vaccination of DTP-HepB-Hib**, respectively:

The seropositivity rate and SCR for all participants will be estimated by groups. The Clopper Pearson method will be used to calculate 95% CIs and the CMH- χ^2 test considering the study site (including Bangladesh 01, Pakistan 01 and Pakistan 02) as a stratification factor will be used to test the differences between groups. The CMH- χ^2 method will be used to calculate the rate difference between (group C2 - group S2) and 95% CIs.

Analysis of covariance model will be modeled to analyze IgG antibody level against PT, FHA and PRN at 28 days after last vaccination of DTP-HepB-Hib. In this model, the log-transformed IgG antibody data against PT, FHA and PRN at 28 days after last vaccination of DTP-HepB-Hib will be included as dependent variable, the log-transformed IgG antibody data before vaccination as a covariate, and treatment group (including C2 and S2) and study site (including Bangladesh and Pakistan) are the fixed effect. From the model, the LS-adjusted log-transformed IgG antibody level against PT, FHA and PRN at 28 days after last vaccination of DTP-HepB-Hib in each group and the difference between (group C2 - group S2) will be calculated. The adjusted GMC at 28 days after last vaccination of DTP-HepB-Hib in each group, GMC ratio between (group C2/group S2), and its 95% CIs will be obtained after inverse log-transformation.

Descriptive statistics, including geometric mean and 95% CIs, for GMC and GMFR of all participants will be presented by groups. The grouped t-test after log-transformation will be used to compare the differences between groups. The ratio of GMC between groups and their 95% CIs will be estimated as well.

The reverse cumulative distribution plot of antibody concentrations at pre- and post-vaccination time points will be plotted.

The above analysis will be based on the FAS and PPS.

➤ **Immunogenicity evaluation for IgG antibodies against diphtheria, tetanus, HepB, Hib and pneumococcal**

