7.10 Subgroup Analysis

Subgroup analysis is planned for both immunogenicity evaluation and safety evaluation in participants of different study country (including Bangladesh and Pakistan).

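### The 12 IgG ANCOVA models in SAP 7.7 define study site as two countries, while the CMH tests beside them and the polio ANCOVA use three sites

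*SAP*

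**What the plan says.** SAP 7.7 gives the site factor in each analysis paragraph, and the content of that factor changes:

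- **Polio ANCOVA (C1 and S1):** "treatment group (including C1 and S1) and study site (including Bangladesh 01, Pakistan 01 and Pakistan 02) are the fixed effect".
- **CMH tests in both IgG subsections (C2 and S2):** "study site (including Bangladesh 01, Pakistan 01 and Pakistan 02) as a stratification factor".
- **ANCOVA in both IgG subsections (C2 and S2):** "treatment group (including C2 and S2) and study site (including Bangladesh and Pakistan) are the fixed effect".

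On randomisation, SAP 4.2 says "Stratified blocked randomization was carried out in this study, taking the study site as a stratification factor", and Protocol 6.3 says "Stratified Blocked Randomization will be carried out, taking the study site as a stratification factor". Neither gives the number of sites. When the SAP means country it uses that word: SAP 7.10 plans subgroup analyses "in participants of different study country (including Bangladesh and Pakistan".

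For geometric means, Protocol 9.3.4 plans no ANCOVA: "The t-tests after log transformation will be used to compare two groups". SAP 7.7 keeps that t-test and an unadjusted ratio, and adds the ANCOVA.

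**The concern.** One label has two contents within one SAP section, and nothing in either document reconciles them. Code written from the IgG paragraphs would drop a factor level that the polio model keeps. Going by the site list in SAP 7.7, that level is a randomisation stratum. An analysis that leaves out a stratification factor usually stays unbiased for the group difference, but any difference between the omitted strata stays in the residual variance. At stake are the confidence intervals of the adjusted GMC ratios for 12 antigens, each in FAS and PPS.

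**Working it through.** **Scope.** PT, FHA and PRN give 3 models. Diphtheria, tetanus, HepB and Hib give 4. Pneumococcal serotypes 1, 5, 6B, 14 and 19F give 5. Total 3 + 4 + 5 = 12.

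**Inputs from the documents.** There are 360 infants per group, with 15% dropout and 10% blood-collection failure (SAP 4.3): 360 × 0.85 × 0.90 = 275.4 evaluable per group. Bangladesh is half of the plan ("Bangladesh and Pakistan, each includes 720 participants", SAP 4.1.1).

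**Assumed inputs.** The documents give no site gap, country gap or SD, so the plan has no figure to reproduce. Let *d* be the gap between the two Pakistani sites in within-site SDs, and *s* the share of Pakistani infants at one of them. The group effect is taken as equal across sites.

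**Effect on the interval.** Blocking within site balances the groups, so *d* drops out of the C2/S2 difference and adds no bias. If the sites are merged, *d* stays in the residual variance for the Pakistani half of the sample:

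inflation = 1 + 0.5 × s(1 − s) × d²; the three-site CI is narrower by 1 − 1/√inflation.

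| d | inflation, s = 0.5 | CI narrower | inflation, s = 0.7 | CI narrower |
|---|---|---|---|---|
| 0 | 1 | 0% | 1 | 0% |
| 0.2 | 1.005 | 0.25% | 1.004 | 0.21% |
| 0.5 | 1.031 | 1.53% | 1.026 | 1.29% |
| 1.0 | 1.125 | 5.72% | 1.105 | 4.87% |

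This formula leaves out the baseline covariate. A simulation that includes it (20,000 runs, 276 per group, sites 138/69/69, baseline correlation 0.3) gave 0.28%, 1.69% and 6.28% for d = 0.2, 0.5 and 1. Coverage was 95.3%, 95.4% and 96.2% with two countries, against 95.2%, 95.0% and 94.8% with three sites. The Monte Carlo SE is 0.15 points, so the two codings cannot be told apart at 0.2 SD. Mean bias was below 0.001 SD.

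**Cost in degrees of freedom.** With 275 per group, the two-country model leaves 550 − 4 = 546 residual df and the three-site model 545.

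**LS-mean weights.** The SAP does not state them. Let B be the Bangladesh mean, and P the mean of P1 and P2 (even split).

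- Two countries, equal weights: (B + P)/2, which matches the planned 720:720.
- Three sites, equal weights: (B + P1 + P2)/3 = (B + 2P)/3, which weights Pakistan 2:1.
- Difference, three sites minus two countries: −(B − P)/6, the same in C2 and S2, so it cancels in the ratio.
- Three sites, observed margins: B/2 + P1/4 + P2/4 = (B + P)/2, so there is no shift.

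If Bangladesh is higher by 0.2, 0.5 or 1 SD and the log10 SD is 0.5, the equal-weight shift in each printed GMC is 10^(−0.5 × 0.2/6) − 1 = −3.8%, then −9.1% and −17.5%. At 0.5 SD it runs from −5.6% to −12.6% for a log10 SD of 0.3 to 0.7.

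**The case against.** The strongest reply is that nothing decided in this trial depends on these models. The only formal hypothesis in SAP 7.6 is polio seroconversion. The protocol's non-inferiority criteria for diphtheria, tetanus and pertussis are on rates, and the SAP's CMH analysis of those rates uses three sites. No margin attaches to any GMC ratio. All of this stands.

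A country term can also be defended. Bangladesh uses PCV10 and Pakistan PCV13 (Protocol Annex). The age windows differ (42–47 and 42–56 days, Protocol 5.1), and Protocol 4.2 recognises age effects on response. But the SAP gives no such reason, it labels the factor study site, and it leaves the polio model on three sites although the age windows apply there too.

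It can be said that each paragraph lists its own levels, so the code is determinate. That is fair, but code that follows the IgG paragraphs then merges two sites under a label that means something else a paragraph earlier. Reading the country list as non-exhaustive does not help, because the same construction introduces the full three-site list elsewhere in the section.

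Two stronger readings are tempting. A reader might infer that the intervals are too wide in any case; that holds only if the two Pakistani sites differ, and the documents do not say whether they do. A reader might also take the 4% to 17% GMC shifts as damage done by the present wording. They are not: they would arise from three-site coding with equal LS-mean weights, and the two-country coding matches the planned country mix.

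**Conclusion.** The inconsistency is real and no other passage resolves it. Its effect is small and confined to secondary GMC results. The adjusted C2/S2 GMC ratio stays unbiased. Its interval is too wide by about 0.3%, 1.5% or 6% if the Pakistani sites differ by an assumed 0.2, 0.5 or 1 SD, and not at all if they are alike. These sizes rest on half the sample being in Pakistan, an even split between its two sites, and no group-by-site interaction. That the merged sites are randomisation strata is inferred from the site list in SAP 7.7.

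The documents do not support reading this as a threat to the primary analysis or to any non-inferiority conclusion. A reader might also infer a larger loss in the Pakistan subgroup, where a two-country factor is constant: with 1 + s(1 − s)d² and s = 0.5, the interval would narrow by 0.5%, 3.0% and 10.6% at the same gaps if sites were fitted. SAP 7.10 does not say that the ANCOVA is repeated there, so this remains conditional. The point is an optional improvement.

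**What to change.** In both IgG ANCOVA paragraphs of SAP 7.7, replace the country list after study site with Bangladesh 01, Pakistan 01 and Pakistan 02, as in the polio ANCOVA. In the same edit, state that LS means use observed-margin (sample-proportional) site weights, so that the adjusted GMCs reflect the enrolled country mix. If country was intended, name the factor study country and give the reason.

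The cost is a few words in the SAP and one model degree of freedom, with no new data and no protocol change. SAP 2.1 has the SAP finalised before database lock, so the edit belongs there. The documents do not show whether lock has passed; if it has, record which coding was used and why.

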4.2 Rationale for Study Design

This study is designed to study the immunogenicity and safety of sIPV co-administered with other routine infant vaccines. According to the national immunization schedule of Bangladesh and Pakistan, sIPV was administered concomitantly with PCV, DTP-HepB-Hib and other vaccines at 6, 10 and 14 weeks old. Thus, this study set up the concomitant vaccination schedule according to the real practice in study area. The primary hypothesis of this study is that the seroconversion rate of polio vaccination when administered concomitantly with routine vaccines is non-inferior to that of being administered alone. The secondary hypothesis is that the sero-protection rates of diphtheria, tetanus, and the seropositivity rate of pertussis when routine vaccines are administered concomitantly with sIPV are non-inferior to those administered without sIPV. Two staggered administration groups were designed in this study, one is administered with sIPV at 6 weeks old as the comparator for the non-inferiority evaluation of immune response to polio; another is administered with routine infant vaccines at 6 weeks old, as the comparator for the non-inferiority evaluation of immune response to diphtheria, tetanus, and pertussis. In that way, effects of age on the immune response after vaccination are avoided.

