3.2 Secondary Objectives

- (1) To evaluate non-inferiority of immune response to diphtheria and tetanus antigens, when routine vaccines are administered concomitantly with sIPV.
- (2) To evaluate non-inferiority of immune response to acellular pertussis antigens, when routine vaccines are administered concomitantly with sIPV.
- (3) To evaluate other immunogenicity against diphtheria, tetanus, acellular pertussis antigens.
- (4) To evaluate other immunogenicity of sIPV, when administered concomitantly with routine vaccines.
- (5) To evaluate the immunogenicity against hepatitis B and Hib, when routine vaccines are administered concomitantly with sIPV.
- (6) To evaluate the immunogenicity against pneumococcal, when routine vaccines are administered concomitantly with sIPV.
- (7) To evaluate other safety in terms of ARs (Vaccine-related AEs).
- (8) To evaluate the safety in terms of Serious Adverse Events (SAEs).

4 Study Design

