7.6 Study Hypothesis

The following research hypothesis will be considered for the immunogenicity evaluation of **group C1** and **group S1**:

➤ **Hypothesis test I:** At 28 days after full vaccination, group C1 will have a non-inferior seroconversion (4-fold increase) rate of Nab against polioviruses to group S1, ie:

$$\text{Null hypothesis } H_0: \pi_{C1j,d28} - \pi_{S1j,d28} \leq \Delta_1$$

$$\text{Alternative hypothesis } H_1: \pi_{C1j,d28} - \pi_{S1j,d28} > \Delta_1$$

Where $j = 3$ serotypes of Nab against polioviruses (including type 1, 2 and 3). $\pi_{C1j,d28}$, and $\pi_{S1j,d28}$ represent the seroconversion (4-fold increase) rate of type- j Nab against polioviruses at 28 days after full vaccination in group C1 and group S1, respectively, with the non-inferiority criterion Δ_1 is -10%, and a one-sided α is 0.025.

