The following analysis will be performed for IgG antibodies against diphtheria, tetanus, HepB, Hib and pneumococcal (including serotypes of 1, 5, 6B, 14 and 19F) of **group C2 and group S2 at 28 days after last vaccination of DTP-HepB-Hib and PCV**, respectively:

The SPR for all participants will be estimated by groups. The Clopper Pearson method will be used to calculate 95% CIs and the CMH- χ^2 test considering the study site (including Bangladesh 01, Pakistan 01 and Pakistan 02) as a stratification factor will be used to test the differences between groups.

Analysis of covariance model will be modeled to analyze IgG antibodies against diphtheria, tetanus, HepB, Hib and pneumococcal (including serotypes of 1, 5, 6B, 14 and 19F) at 28 days after last vaccination of DTP-HepB-Hib. In this model, the log-transformed IgG antibodies against diphtheria, tetanus, HepB, Hib and pneumococcal (including serotypes of 1, 5, 6B, 14 and 19F) at 28 days after last vaccination of DTP-HepB-Hib will be included as dependent variable, the log-transformed IgG antibody data before vaccination as a covariate, and treatment group (including C2 and S2) and study site (including Bangladesh and Pakistan) are the fixed effect. From the model, the LS-adjusted log-transformed IgG antibodies against diphtheria, tetanus, HepB, Hib and pneumococcal (including serotypes of 1, 5, 6B, 14 and 19F) at 28 days after last vaccination of DTP-HepB-Hib in each group and the difference between (group C2 - group S2) will be calculated. The adjusted GMC at 28 days after last vaccination of DTP-HepB-Hib in each group, GMC ratio between (group C2/group S2), and its 95% CIs will be obtained after inverse log-transformation.

Descriptive statistics, including geometric mean and 95% CIs, for GMC and GMFR of all participants will be presented by groups. The grouped t-test after log-transformation will be used to compare the differences between groups. The ratio of GMC between groups and their 95% CIs will be estimated as well.

The reverse cumulative distribution plot of antibody concentrations at pre- and post-vaccination time points will be plotted.

The above analysis will be based on the FAS and PPS.

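### SAP 7.7 drops the C2−S2 rate difference, its 95% CI and the −10% rule for diphtheria and tetanus, so the SAP text plans no output that decides that non-inferiority objective

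*SAP*

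**What the plan says.** **Protocol.** Section 4.2 makes this a formal hypothesis: "The secondary hypothesis is that the sero-protection rates of diphtheria, tetanus, and the seropositivity rate of pertussis" under co-administration are to be non-inferior to those without sIPV. Section 9.3.4 has one block headed "Analysis for immunogenicity against Diphtheria, Tetanus, Pertussis". It plans Clopper-Pearson intervals per group, a CMH test stratified by site, and then the "rate difference between (group C2 and group S2) and 95% CIs. Non-inferiority will be concluded if the lower limit of the 95% CI" of the difference is above −10%. Hepatitis B, Hib and pneumococcal have a separate block with no non-inferiority rule.

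**SAP.** Section 3.2 keeps the objective: "To evaluate non-inferiority of immune response to diphtheria and tetanus antigens, when routine vaccines are administered concomitantly with sIPV". Section 7.7 then puts diphtheria and tetanus under "Immunogenicity evaluation for IgG antibodies against diphtheria, tetanus, HepB, Hib and pneumococcal". For the rates, that block says "The SPR for all participants will be estimated by groups. The Clopper Pearson method will be used to calculate 95% CIs", followed by a CMH test with study site "as a stratification factor will be used to test the differences between groups". The rest of the block (ANCOVA, GMC ratios, t-tests, GMFR, reverse cumulative plots) concerns concentrations and carries no non-inferiority criterion.

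Section 7.6 opens with "The following research hypothesis will be considered for the immunogenicity evaluation of" groups C1 and S1 and states the polio hypothesis only. Section 7.11 refers back to 7.6 as the polio hypothesis. Section 2.3 says the planned analyses are consistent with the protocol.

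**The concern.** The SAP keeps a non-inferiority objective but not the quantity that decides it. The protocol's rule needs the lower limit of a site-stratified 95% CI for the C2−S2 difference, and the SAP text plans that number for neither diphtheria nor tetanus. A reader can subtract the two group rates, but cannot recover the stratified interval from the planned output. The country subgroup tables in SAP 7.10 give two strata, whereas the analysis uses three sites. The CMH p-value addresses a different question, because p > 0.05 can occur with the margin missed.

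The SAP does not simply predate the rule. SAP V1.0 is dated 28 October 2024. The last protocol version in the change log, which lists a revision of 9.3.4, is dated 27 March 2024. If the difference and its interval are added only once results are known, their place in the SAP as a planned analysis will be open to question.

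**Working it through.** **1. The texts side by side (rates only)**

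| Output | Protocol 9.3.4, diphtheria/tetanus | SAP 7.7, polio | SAP 7.7, pertussis | SAP 7.7, diphtheria/tetanus |
|---|---|---|---|---|
| Rate per group, Clopper-Pearson CI | yes | yes | yes | yes |
| Site-stratified CMH test | yes | yes | yes | yes |
| Rate difference with 95% CI | yes | yes | yes | **no** |
| Lower limit > −10% rule | yes | yes | no | **no** |
| Hypothesis in SAP 7.6 | – | yes | no | **no** |

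For pertussis the deciding interval is planned and only the rule is not restated, which is a minor gap. For diphtheria and tetanus both are absent.

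**2. Sample sizes used below.** The documents' only calculation is for polio: 233 per group, from 90% in both arms, a 10-point margin, one-sided alpha 0.025 and power 1 − 0.20/3 = 93.3%.

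- The Farrington-Manning score formula gives 231.8, so 232, which is within one of 233. The unpooled formula gives 216.
- Nothing comparable is given for diphtheria or tetanus.
- Applying the stated losses to the planned 360 gives 360 × 0.85 × 0.90 = 275.4, so 275 evaluable per arm. The range 233 to 360 is also shown.

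**3. Can the planned test stand in for the rule?** Method: unstratified, with a pooled z test and an unpooled (Wald) 95% interval. The counts are assumed: 234/275 in C2 and 248/275 in S2.

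- Difference: 0.8509 − 0.9018 = −0.0509.
- Test: pooled rate 482/550 = 0.8764; SE = √(2 × 0.8764 × 0.1236/275) = 0.0281; z = −1.81; p = 0.070.
- Interval: SE = √(0.8509 × 0.1491/275 + 0.9018 × 0.0982/275) = 0.0280; lower limit = −0.0509 − 1.96 × 0.0280 = −0.106.

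The test is not significant and the rule fails. Conversely, 258 versus 269 of 275 gives p = 0.019 with lower limit −7.3%: the test is significant and the rule is met. The second pattern is no error, but together the two show that the p-value does not sort outcomes the way the rule does.

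**4. How often is p > 0.05 with the margin missed?** Exact sums over two independent binomials, 275 per arm, all true rates assumed:

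| True control rate | Equal rates | 5-point loss | 10-point loss |
|---|---|---|---|
| 80% | 14% | 42% | 20% |
| 85% | 6.8% | 32% | 13% |
| 90% | 0.6% | 14% | 6.0% |
| 92% | 0.03% | 5.0% | 3.0% |
| 95% | near 0 | 0.03% | 0.14% |

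At 90% with a 5-point loss, the figure is 24% for n = 233, 14% for n = 275 and 0.7% for n = 360. At n = 275 the pattern can arise only when the observed control rate is about 92% or lower (253/275 at most).

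**5. What the rule would deliver.** With equal true rates and n = 275, the probability that the lower limit exceeds −10% is 83% at 80%, 91% at 85%, 97% at 90% and 99.9% at 95%, per antigen.

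**The case against.** The objective is secondary, and the primary polio hypothesis, the sample size and the data are untouched. Protocol 9.3.4 still fixes the estimator, interval and margin, so nobody is free to choose a margin after seeing the data. The claim of consistency in SAP 2.3 points to a drafting slip, not a decision to drop the test. The mock-up shells named in SAP 2.1 are not among the documents and may contain the difference. Nothing in the SAP says that p > 0.05 will be read as non-inferiority.

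One criticism of the figures also stands. In the equal-rate and 5-point-loss columns the true difference lies inside the margin, so those probabilities describe trials that are inconclusive on non-inferiority while the test shows no difference. They are not false claims about a truly inferior regimen. The 10-point-loss column is the relevant one for that, and at control rates of 80% to 92% it is smaller than the 5-point column (20% against 42% at 80%, for example).

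These points limit the consequences. They do not supply the missing output: no other SAP section plans it. Shells could not correct 7.6 or 2.3 either.

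**Conclusion.** The concern holds as a statement about the SAP text. Followed as written, SAP 7.7 yields per-group rates and a test of difference for diphtheria and tetanus, and neither can decide the non-inferiority objective that SAP 3.2 retains. The departure from protocol 9.3.4 is undeclared, and SAP 2.3 is wrong on this point.

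This conclusion rests on comparing the texts, not on assumed rates. The size of the practical effect does depend on rates that the documents do not give, and on unstratified calculations. At control rates around 80% to 90%, a non-significant test would often coexist with a missed margin. At 95% or above it almost never would, and the loss is then a non-inferiority conclusion the trial would very probably have reached. The omission should be corrected before database lock; the documents do not show whether lock has taken place.

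**What to change.** 1. In SAP 7.7, for diphtheria and tetanus sero-protection, add the site-stratified C2−S2 rate difference with its 95% CI, and the protocol 9.3.4 rule that the lower limit must exceed −10%.
2. In SAP 7.6, add the C2 versus S2 hypotheses for diphtheria and tetanus sero-protection and for PT, FHA and PRN seropositivity, with the −10% margin judged on the lower limit of the two-sided 95% CI. Restate the rule for the three pertussis antigens in 7.7.
3. Correct SAP 2.3. If the omission was intended, declare and justify it there.

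The cost is SAP wording and a small set of table changes (FAS and PPS, plus the country subgroups of SAP 7.10). No new data, visits or participants are needed.
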